****TAY Exiting the Adult Criminal System (ADULT POPULATION)****

Study population:

Participants who are eligible for the Whole Person Care—Los Angeles (WPC-LA) Reentry post-release program will be eligible for the adult population of this study. The WPC Reentry program, implemented by the Los Angeles County Health Services Department, links jail inmates with community-based health, behavioral health, and social service providers as they return to the community. The intervention connects participants to Community Health Workers (CHWs) with a prior personal history of incarceration. CHWs assist participants in engaging with community-based health, behavioral health, and social service providers during reentry to the community. Services provided include mentorship and social support; health and social service navigation; linkage to housing, employment, education, legal assistance and social supports; accompaniment to key health and behavioral health appointments; assistance with adherence to appointments, treatments and medications; and connection to transportation. The mentorship and social support aspects of the intervention will indirectly target the social networks of participants. The WPC intervention is an existing intervention. The WPC intervention enrolls 750 individuals per month across LA County; approximately 12% are transition age youth ages 18-24. Participants are invited to this program while detained by the WPC case manager. Thus, WPC is a voluntary program. The WPC case manager is responsible for determining eligibility for the WPC reentry program and enrollment in the WPC program, not the research staff.

Recruitment and Consent:

We will recruit 160 adults exiting the LA county justice system – 80 who have enrolled in the WPC program and 80 have not. We anticipate enrolling participants over an approximate 9 month window, aiming to recruit about 9 individuals per arm (WPC and non-WPC) each month. This represents approximately 10% of the eligible population each month for each arm.

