## **STATISTICAL DESIGN AND POWER**

### **Analytic Strategy**

For each of the aims, we will compare participants who received WPC pre-release services (control group) to participants who received WPC pre-release and post-release services (intervention group). To address possible differential uptake or attrition, we will also conduct treatment received analyses, using the percent time young people participated in the post-release program (9 months total for the initial cohort and 6 months total for the final cohort) as the predictor of outcome. We will also examine for balance on sociodemographic variables and other characteristics of interest between the intervention and control groups as a means of examining for selection bias. To address missing data, in the main analysis, we will use generalized mixed effects model for repeated measures, under the missing-at-random assumption. In addition, using multiple imputations with pattern-mixture models, we will conduct sensitivity analyses to investigate whether our findings are robust to the missing mechanisms (i.e., assuming missing-not-at-random). In particular, we will consider a scenario which is least favorable to the intervention arms; that is, a scenario where the missing observations in the intervention arm follow the same pattern as the one in the control arm.

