#### **Aim 1: Measure the impact of the WPC Reentry intervention targeting recently incarcerated young people on decreasing rates of 30-day use and risky use of marijuana, alcohol, and other drug use.**

*Hypothesis 1:* Young people receiving the WPC intervention will have less substance use at follow-up (3 and 9 months for initial cohort, and 4 and 6 months for final cohort) compared to their in the control group.

For the main outcome, percentage of days used marijuana in the last 30 days, we will conduct a linear mixed effects regression model to account for repeated measurements within individual young people. We will perform unadjusted and adjusted comparisons, controlling for baseline demographic (race/ethnicity, age, parental SES) and substance use characteristics, as well as any variables found to be differential between the intervention and control groups. Similar analyses will be carried out to examine the impact of WPC on percentage days used alcohol and other drugs, and risky use of marijuana, alcohol, and other drugs. We will estimate the treatment effect on marijuana use with the adjustment of incarceration based on the principle stratification analysis.

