#### **Aim 2: Test whether the WPC Reentry intervention decreases recidivism, increases receipt of behavioral health services, improves mental health, and enhances school and work engagement (secondary outcomes).**

*Hypothesis 2:* Young people receiving the WPC intervention will have less recidivism and mental health symptoms, and higher rates of receipt of community behavioral health services and school and work engagement.

For each of the secondary outcomes, recidivism, mental health symptoms, receipt of behavioral health services, and school and work engagement, we will conduct generalized linear mixed effects regression models to account for repeated measurements within individual young people, while controlling for baseline demographic and substance use characteristics, as well as any variables found to be differential between the intervention and control groups. We will also evaluate whether there is effect modification by baseline mental health symptoms, using interaction terms with the exposure variable in the regression analysis.

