Primary social network measures will include the change in proportion of peers using substances (alcohol, marijuana, other drugs), limited to those whom the subject interacts with within the last month. We will compare baseline social network characteristics of the intervention and control groups and control for these measures if significant differences are noted. To test whether young people receiving WPC report a lower proportion of peers in their network engaging in substance use, we will conduct a mixed effects binomial logistic regression model accounting for repeated measurements within students. We will control for baseline demographic characteristics, as well as any variables found to be differential between the intervention and control groups. We will also examine the number of non-using supportive adults in their network using a mixed effects binomial logistic regression model. Finally, based on young peoples' descriptions of the connections between alter-alter pairs, we will construct a measure of peer network density (number of alter-alter connections out of total possible) for the peer substance-using and non-using networks. We will use mixed effects models to investigate whether network structure differs between study arms and whether intervention young people report stronger connections to healthy peers and adults.

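### Beyond a short core set, confounders enter the models only if the self-selected arms are found to differ; the adjustment set should be fixed in advance

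*SAP*

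**What the plan says.** The comparison is not randomised. The Protocol's section on the adult population states "Thus, WPC is a voluntary program" and plans 160 adults, "80 who have enrolled in the WPC program and 80 have not". Under Recruitment and Consent, a participant's own decision to opt in or out determines the study group.

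The SAP sets the adjustment rule aim by aim:

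- **Aim 1:** "controlling for baseline demographic (race/ethnicity, age, parental SES) and substance use characteristics" is always done. Further covariates follow the rule "as well as any variables found to be differential between the intervention and control groups".
- **Aim 2:** the same structure, "while controlling for baseline demographic and substance use characteristics, as well as any variables found to be differential between the intervention and control groups".
- **Aim 3, peer-network model:** "We will control for baseline demographic characteristics, as well as any variables found to be differential between the intervention and control groups". Baseline substance use is not in this fixed set. For baseline network characteristics the SAP will "control for these measures if significant differences are noted".

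The Analytic Strategy adds a balance check "as a means of examining for selection bias". These sections give no list of candidate covariates, no threshold for Aims 1 and 2, and no propensity or weighting method.

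**The concern.** When people select their own arm, a covariate matters because it is related to both uptake and outcome, not because a test in this sample detected a difference. With about 80 per arm, a screen on observed differences has limited power for small to moderate imbalances. It can therefore leave out a variable whose omission shifts the estimated WPC effect. It also lets the data choose the model. Since the SAP does not define what counts as differential in Aims 1 and 2, the analyst has discretion after seeing the data.

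Baseline mental health shows the gap. The SAP treats it as a possible effect modifier in Aim 2, yet it is not in any fixed adjustment set. The gap is wider in Aim 3, where the outcomes are peer substance use and network composition but neither baseline substance use nor baseline networks are sure to be adjusted for.

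The survey covariates also carry more weight than first planned. The Protocol meant to use chart data as covariates for group differences, but the 10/28/20 amendment dropped chart abstraction.

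**Working it through.** **Inputs from the SAP, Sample Size Estimate:** 160 participants, 10% attrition at 3 months, two-sided alpha 0.05, 80% power, detectable difference 17 percentage points. This gives 80 per arm enrolled and 80 × 0.9 = 72 per arm analysed.

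**Assumed:** a screen at p<0.05 in all aims; confounder correlations of 0.4 to 0.5 with the outcome; imbalances in SD units as shown.

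**1. The plan's own figure.** No outcome SD is stated, so the 17 points cannot be reproduced independently. Solving backwards at 72 per arm: SD = 17 / [(1.960 + 0.842) × √(2/72)] = 17 / 0.467 = 36.4 points. With an SD of 30 the detectable difference would be 14.0, and with 40 it would be 18.7. The biases below scale in proportion to the SD.

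**2. How often the screen misses a true imbalance.** For a two-sample t test with noncentrality d × √(n/2), at d = 0.3 and n = 80 this is 0.3 × √40 = 1.90 against a critical value of 1.98. The miss probability is 0.529.

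| True imbalance (SD) | Missed, 80 per arm | Missed, 72 per arm | Missed, 80 per arm, alpha 0.10 |
|---|---|---|---|
| 0.2 | 76% | 78% | 65% |
| 0.3 | 53% | 57% | 40% |
| 0.4 | 29% | 34% | 19% |
| 0.5 | 12% | 15% | 6–7% |

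(The alpha 0.10 column uses the normal approximation.) With three independent confounders at 0.3 SD and 80 per arm, at least one is missed with probability 1 − (1 − 0.529)³ = 0.90.

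**3. Average bias under the screen.** Bias arises only in samples where the covariate is left out, and those samples have smaller observed imbalances. At 80 per arm the observed imbalance D has mean 0.3 and standard error √(2/80) = 0.158. It escapes the screen when |D| < 1.96 × 0.158 = 0.310. In those samples D averages 0.180. Multiplied by the miss probability (0.525 by normal approximation), the average unadjusted imbalance is 0.0946 SD. At 72 per arm it is 0.1034 SD.

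Bias = unadjusted imbalance × correlation × 36.4:

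- One confounder, 80 per arm: 0.0946 × 0.4 × 36.4 = 1.4 points; with correlation 0.5, 1.7 points.
- One confounder, 72 per arm: 1.5 and 1.9 points.
- Three confounders with joint correlation 0.5, so 0.5/√3 = 0.289 each: 3 × 0.0946 × 0.289 × 36.4 = 3.0 points at 80 per arm, 3.3 at 72.

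**4. Type I error, by simulation.** With no true effect, one follow-up, no other covariates and 10,000 runs per case, the screen gave 0.054 to 0.058 for one confounder at 0.3 SD and 0.081 to 0.086 for three. Always adjusting gave 0.047 to 0.052, with bias of at most 0.1 point.

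**5. Allowing for baseline substance use.** A simulation at 72 per arm also adjusted for baseline use (assumed correlations 0.5 with the outcome and 0.3 with the confounder). For one confounder with raw correlation 0.3 to 0.5, average bias was 0.6 to 1.4 points, and type I error was 0.050 in the central case.

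**The case against.** The strongest reply is that Aims 1 and 2 already adjust for demographics and baseline substance use, and the latter is probably the best single predictor of later marijuana use. What matters is the association a confounder keeps after that adjustment. This stands, and step 5 shows the effect is then smaller. It does not cover the Aim 3 peer-network model, whose fixed set is demographics only.

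Second, the wording in Aims 1 and 2 does not mention a significance test. A threshold on standardised differences would also satisfy it. This stands too: the miss rates for those aims depend on an assumed screen. But the criterion is then undefined, and the covariates could still be chosen after seeing the data.

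Third, a reader might infer that because the fixed sets omit serious mental illness, homelessness and chronic illness, which are among WPC's qualifying conditions, the arms must differ on them. The documents do not support that. Every adult participant in either group must be WPC-eligible (Protocol, inclusion criteria), and the SAP's Analytic Strategy has both arms receiving pre-release services. The mix of conditions could differ between arms, but nothing shows that it does.

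Finally, the Protocol describes an exploratory, observational pilot, and unadjusted results will be reported beside adjusted ones. That limits the consequences but is no reason to prefer a data-driven rule when a fixed one costs so little.

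**Conclusion.** The point holds in a limited form. In a self-selected comparison, the SAP makes adjustment beyond the core set depend on an observed difference between arms, and a fixed set would be better. Under an assumed 0.05 screen, imbalances of 0.2 to 0.3 SD are missed more often than not, while those of 0.5 SD or more are usually caught.

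Average bias at 0.3 SD is roughly 1.5 to 2 points for one confounder (9% to 12% of the 17-point target) and about 3 points for three (18%). Type I error is about 0.06 and 0.08 respectively. These figures rest on the assumed correlations, the back-solved SD and the assumed screen. They shrink where the confounder overlaps with baseline substance use. The bias could favour or disfavour WPC.

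Two stronger readings should be set aside. A reader might take the bias to be 0.3 × 0.4 × 36.4 = 4.4 points, about a quarter of the target. That applies only if the covariate is never adjusted for, whereas under the screen the larger observed imbalances are adjusted. A reader might also infer that confidence intervals will be materially too narrow. With one confounder the type I error barely leaves 0.05, and with three the excess is modest.

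**What to change.** Replace the conditional rule in Aims 1, 2 and 3 with a named adjustment set for each aim, used regardless of any baseline comparison. Keep the existing demographics and baseline substance use, and add baseline substance use to Aim 3. Add baseline mental health symptoms, behavioral health service use and baseline network composition, drawing on what the baseline survey collects. Include homelessness and prior incarceration only if the survey captures them: with chart abstraction dropped, the documents do not show that it does. Report balance as standardised differences, for description only.

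The cost is SAP wording and a few model degrees of freedom at about 144 analysed. No new data collection is needed for variables already surveyed. Unmeasured motivation to enrol remains, and no covariate list removes it. Label: cheap improvement.

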#### **Aim 2: Test whether the WPC Reentry intervention decreases recidivism, increases receipt of behavioral health services, improves mental health, and enhances school and work engagement (secondary outcomes).**

*Hypothesis 2:* Young people receiving the WPC intervention will have less recidivism and mental health symptoms, and higher rates of receipt of community behavioral health services and school and work engagement.

For each of the secondary outcomes, recidivism, mental health symptoms, receipt of behavioral health services, and school and work engagement, we will conduct generalized linear mixed effects regression models to account for repeated measurements within individual young people, while controlling for baseline demographic and substance use characteristics, as well as any variables found to be differential between the intervention and control groups. We will also evaluate whether there is effect modification by baseline mental health symptoms, using interaction terms with the exposure variable in the regression analysis.

#### **Aim 3: Examine whether recently incarcerated receiving the WPC intervention report healthier social networks (lower proportion of peers engaging in risky behaviors and a higher number of supportive adults) than control young people.**

*Hypothesis 3:* Young people receiving the WPC intervention will have a lower proportion of peers engaging in substance use and a higher number of supportive adults in their social networks, compared to young people in the control group.

Regardless of whether WPC lowers drug use, recidivism, or use of support services, the social network analysis of reentry young people will give valuable information on changes in social networks among recently incarcerated young people during reentry. In addition, WPC is designed to encourage prosocial peer network formation, and the social network analysis will help determine why the intervention did or did not demonstrate the expected effect. Understanding strategic levers for how young peoples' social networks can be altered is critical to developing sustaining solutions to young people substance use and incarceration. We will measure how social networks function for young people and whether the insertion of a supportive adult can create linkages to substance use services and promote healthier social networks. We will use the approach described in Baron and Kenny (1986) to evaluate whether our data are consistent with a model in which social networks mediate the relationship between WPC receipt and substance use. Additionally, if analyses for Aims 1 and Aim 2 do not indicate improvement overall in the intervention group, we will conduct exploratory analyses to identify subgroups of young people whose Aim 1 and Aim 2 outcomes improve and examine their social networks.

Primary social network measures will include the change in proportion of peers using substances (alcohol, marijuana, other drugs), limited to those whom the subject interacts with within the last month. We will compare baseline social network characteristics of the intervention and control groups and control for these measures if significant differences are noted. To test whether young people receiving WPC report a lower proportion of peers in their network engaging in substance use, we will conduct a mixed effects binomial logistic regression model accounting for repeated measurements within students. We will control for baseline demographic characteristics, as well as any variables found to be differential between the intervention and control groups. We will also examine the number of non-using supportive adults in their network using a mixed effects binomial logistic regression model. Finally, based on young peoples' descriptions of the connections between alter-alter pairs, we will construct a measure of peer network density (number of alter-alter connections out of total possible) for the peer substance-using and non-using networks. We will use mixed effects models to investigate whether network structure differs between study arms and whether intervention young people report stronger connections to healthy peers and adults.

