Potential subjects will be identified as follows: (1) The research associate (RA) will shadow the WPC case manager as she invites participants to enroll in WPC. (2) The RA will then approach and ask potential WPC participants if they are interested in participating in the study, regardless of whether they accept to enroll in the WPC program or not. If the participant opts in to the WPC intervention, he/she will be placed in the “intervention” group of the study; if the participant opts out of the WPC intervention, he/she will be placed in the “non-intervention” group of the study. (3) If the participant is interested in participating in the study, the RA will confirm the age of the participant (must be between the ages of 18-24) and assess whether there are no severe cognitive delays based on communication with the participant.

If eligible, the RA will review the study with the interested participant and obtain written consent. Furthermore, the RA will obtain a signed HIPAA authorization form for research for medical record access to allow for later record review and abstraction. The RA will remind the participant of the voluntary nature of the study and that participation in no way affects their standing with the Court, the Sheriff’s department, or their receipt of WPC.

Data Collection:

The RA will administer the baseline survey in a private area where respondents’ answers cannot be overheard. Surveys have been piloted with TAY not in jail and take an average of 20 minutes to complete. Upon completion of the survey, the RA will ask for a telephone number and address to contact the participant after their release from incarceration. This information will be kept separate from the survey. To encourage follow-up, a \$50 cash or gift card incentive (based on participant’s preference) will be given to participants if they contact the research team after their release. At this time, participants will also be provided with a copy of the consent and HIPAA authorization forms.

Follow-up surveys will be conducted at 3 and 9 months post-release. These surveys will be conducted in-person or over the phone, based on participant’s preference, and are expected to last up to 30-minutes each. A \$50 gift card or cash incentive will be given after the completion of each follow-up survey.

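### Aim 3 names a change in the proportion of substance-using peers but tests a level, with no stated time contrast and baseline networks adjusted for only if significantly different

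*SAP*

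**What the plan says.** The SAP, under Aim 3, defines the measure as a change: "Primary social network measures will include the change in proportion of peers using substances". The sentence that introduces the model asks about a level: "To test whether young people receiving WPC report a lower proportion of peers in their network engaging in substance use". Hypothesis 3 is also a level: "Young people receiving the WPC intervention will have a lower proportion of peers engaging in substance use".

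The model is given as "we will conduct a mixed effects binomial logistic regression model accounting for repeated measurements within students". The covariates are given as "We will control for baseline demographic characteristics, as well as any variables found to be differential between the intervention and control groups". For baseline network characteristics, the team will compare the groups and "control for these measures if significant differences are noted". The section does not say whether the baseline survey is one of the repeated outcomes, whether survey time is in the model, or which coefficient is the test.

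The Protocol (Research Design and Methods, Statistics and Data Analysis) has the same measure and model, apart from a different peer-contact window. On allocation, the Protocol's adult recruitment text says "if the participant opts out of the WPC intervention, he/she will be placed in the “non-intervention” group of the study". The SAP's Analytic Strategy describes the control group differently, as recipients of pre-release services only, but it too treats selection bias as something to be examined.

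**The concern.** A binomial logistic model takes as its response a count of using peers out of peers named at one survey. It addresses change only through a contrast over time, and none is named. At least three analyses fit the text: one arm coefficient over all surveys, one arm coefficient over follow-up surveys, and an arm-by-time contrast. They answer different questions.

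In a randomised trial the last two would target much the same effect. Here, people who choose WPC may already have different networks. A change measure removes a stable starting gap, while a level measure keeps whatever part of the gap is not adjusted away. What is at stake is whether Aim 3 can separate a network change under WPC from a network difference that preceded it. There is also room to choose among the contrasts after the data are seen.

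**Working it through.** **No plan figure to reproduce.** The only power statement (SAP, Sample Size Estimate) concerns days of marijuana use. It supplies N = 160 and 10% attrition. With 80 per arm from the Protocol, 80 × 0.9 = 72 evaluable per arm. All other inputs below are assumptions.

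**Step 1: what each contrast estimates.** Take three surveys (baseline and two follow-ups), ignore the person effect, and hold the control group at 50% using peers throughout. The odds ratio for 40% v 50% is (0.4/0.6)/(0.5/0.5) = 0.67, with log −0.405. For 60% v 50% it is 1.5, with log +0.405. The pooled arm coefficient is close to the average of the three log odds ratios.

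| WPC group at the three surveys | Pooled over all surveys | Follow-up only | Arm-by-time |
|---|---|---|---|
| 50%, 40%, 40% (true improvement) | 0.76 | 0.67 | 0.67 |
| 40%, 40%, 40% (gap, no change) | 0.67 | 0.67 | 1.00 |
| 60%, 50%, 50% (starts worse, improves) | 1.14 | 1.00 | 0.67 |

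Check on the pooled column, row 1: (0 − 0.405 − 0.405)/3 = −0.270, and exp(−0.270) = 0.76. Row 3: (0.405 + 0 + 0)/3 = 0.135, and exp(0.135) = 1.14. The choice of contrast can therefore alter the size, the presence or the direction of the effect.

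**Step 2: dilution by pooling.** With one baseline among three surveys, about 1/3 of the effect is lost. With one among four, about 1/4 is lost. Simulation with 72 per arm, about 7 peers per survey, a person random-intercept SD of 1 and a 50% to 40% effect agrees:
- two follow-ups: −0.23 against −0.34, and 1 − 0.23/0.34 = 0.32
- three follow-ups: −0.25 against −0.33, and 1 − 0.25/0.33 = 0.24

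The simulated coefficients are population-averaged, so they lie nearer zero than −0.405.

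**Step 3: false positives under the plan's adjustment rule.** The set-up is the same, with a stable 50% v 40% gap, no WPC effect and two-sided 5% tests. Ranges cover two and three follow-ups and repeat runs of 500 to 1,000 trials.

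| Analysis | Significant |
|---|---|
| Level, baseline never adjusted | 51-63% |
| Level, baseline adjusted only if significantly different | 29-35% |
| Level, baseline always adjusted | 22-29% |
| Arm-by-time | 5-7% |

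The conditional rule falls short because the baseline comparison detects the gap in only 41-48% of trials. With half the gap, the rule gives 11-13%, against about 5% for arm-by-time.

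**Step 4: the price of arm-by-time.** With equal baselines and a true effect, its power is about 57-67%, against 74-84% for follow-up proportions always adjusted for baseline.

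The fits were population-averaged binomial models with person-clustered standard errors, standing in for the mixed model.

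**The case against.** The SAP lists no fixed effects beyond covariates, so a reader who infers that arm-by-time is excluded takes silence for a decision. That objection stands: the term is unspecified, not ruled out. Nor is the model family an obstacle. The same binomial mixed model, with baseline among the outcomes and an arm-by-time term, estimates a difference in change on the log-odds scale. As a level model it also matches Hypothesis 3.

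The plan does provide for baseline differences, so the 51-63% for no adjustment at all is not a fair description of it. The conditional rule roughly halves that rate. Part of what remains comes from non-random groups and a significance-triggered rule, and would persist under clearer wording about change and level.

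Arm-by-time is not plainly superior either. Change and baseline-adjusted analyses are both standard, and they rest on different assumptions when groups are not randomised. The simulated gap is stable by construction, which favours arm-by-time.

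It is also tempting to say that WPC cannot have acted by baseline. That suits the in-jail baseline. Under the 10/28/20 amendment, baseline is 2 weeks after release, and the SAP defines the intervention by its post-release services. Nineteen participants were enrolled at the May 2020 amendment. If 160 is reached, up to 160 − 19 = 141 could have the later baseline, and subtracting a partly treated baseline would dilute the effect.

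These points limit the claim and widen the choice of remedy. They do not reconcile the measure with the test.

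**Conclusion.** The point holds as an unreconciled estimand with unspecified baseline handling, and it should be corrected for Aim 3. Under the plan's conditional rule, a level contrast would call a stable 50% v 40% starting gap a WPC effect in about 29-35% of trials, against about 5-7% for arm-by-time. Pooling one arm coefficient over baseline and follow-up would lose about one quarter to one third of a true effect. These sizes depend on the assumed gap, peer count and person SD, none of which the documents give.

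Two stronger inferences are not supported. The documents do not show that the planned model must test the wrong quantity, since that depends on terms left unstated. They also do not say that the mediation analysis uses this model: the Baron and Kenny approach is described separately. The marijuana-days outcome and the sample size are unaffected.

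**What to change.** State one estimand in SAP Aim 3 and in the Protocol's statistics section.

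- **If change is meant, as the named measure implies:** model the number of using peers out of peers named at each survey, baseline included, with arm, survey time and arm-by-time. Make arm-by-time (baseline versus follow-up) the test, and name the visit or visits it refers to.
- **If a level is meant:** remove change from the measure, model follow-up surveys only, and always adjust for the baseline proportion. State that this does not fully remove a pre-existing gap.

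In either case, do not let the handling of baseline networks depend on a significance test, and rule out a single arm coefficient pooled over baseline and follow-up as the test. If arm-by-time is chosen, state its lower power when the arms start equal and the possible dilution in the final cohort.

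The cost is a sentence or two in each document, with no new data and no change of software.
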